STUDY TITLE:

**“VALUE OF TEMPORARY OCCLUSION OF THE
UTERINE ARTERIES IN LAPAROSCOPY
MYOMECTOMY”**

INVESTIGATOR: [name] [name]. Head of the Gynecology Section.
Ramon y Cajal Hospital in Madrid.

CENTER: RAMÓN Y CAJAL UNIVERSITY HOSPITAL

Address: [name].

Gynecology Service

Email: [contact]

[contact]

SUMMARY:

1. Objectives:

- Main objective: To analyze the patients who underwent a laparoscopic myomectomy, to assess whether there are significant differences in terms of a decrease in intraoperative blood loss between patients with temporary clamping of the uterine arteries and utero-ovarian ligaments and patients without temporary occlusion during the surgical technique.

- Secondary objectives: To determine the surgical time of each technique, the improvement of the symptoms for which the patient is operated, the length of hospital stay and the possible complications of each technique.

2. Methods:

- **Study design** : This is a randomized prospective longitudinal clinical trial in patients with fibroids who require surgery, from the Gynecology service of the Ramón y Cajal Hospital.

- **Study population and total number of subjects** :

A total of 37 patients who underwent laparoscopic myomectomy with temporary occlusion of the uterine arteries and utero-ovarian ligaments using clips will be analyzed with a control group of 37 patients who underwent laparoscopic myomectomy with the traditional technique (surgery without temporary occlusion of uterine arteries).

The sample size has been calculated based on data published in the literature, where there is a difference in hemoglobin levels of 0.7 g/dl between the two groups, with a statistical power of 80% and an alpha error of 5%.

1. INTRODUCTION.

Uterine fibroids are the most frequent benign tumors originating in smooth muscles of the female genital tract.

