2. GOALS

Main objective :

- To identify the efficacy of temporary occlusion of the uterine arteries during laparoscopic myomectomy by comparing blood loss (by assessing pre- and postoperative hemoglobin in g/dL and intraoperative blood aspirate in milliliters), in 2 groups of patients with symptomatic fibroids undergoing laparoscopic surgery, one with temporary occlusion of uterine arteries and uteroovarian ligaments and one without such occlusion.

Secondary objectives:

- Compare the surgical time of each technique.
- Compare the need for transfusion between both groups.
- Compare the improvement of the symptoms for which the patient is operated.
- Compare the length of hospital stay in each group
- Compare possible complications of each technique.

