3. METHODOLOGY

3.1. DESIGN : Longitudinal prospective randomized clinical trial.

3.2. SUBJECTS OF STUDY : Patients with symptomatic fibroids who require surgery to treat them, from the Gynecology Service of the Ramón y Cajal Hospital. Patients will be randomized into 2 groups: exposed (patients with temporary occlusion of the uterine arteries by clips during surgery) and non-exposed (patients without temporary occlusion of the uterine arteries during surgery).

A patient will be recruited in the pre-surgical consultation when laparoscopic myomectomy is indicated, randomizing both groups by simple random sampling. An informed consent will be delivered to the patients, who have to accept and sign in order to participate in the study. The diagnosis of the presence of fibroids will be made by abdominal and/or transvaginal gynecological ultrasound and/or nuclear magnetic resonance. Fibroids will be quantified, measured and their location described.

3.3. INCLUSION CRITERIA : The inclusion criteria to participate in the study are the existence of uterine fibroids with an indication for laparoscopic surgery and the patient's desire to preserve the uterus.

3.4. EXCLUSION CRITERIA : Patients who do not meet the inclusion criteria, women with symptomatic fibroids who are not candidates for laparoscopic surgery and/or do not

wish to preserve the uterus, those patients who, despite having indications for randomization, do not have the technical possibility of clipping during the intervention.

3.5. VARIABLES TO STUDY : The patients included in the study will have their pre-surgical hemoglobin determined by preoperative analysis and another post-surgical hemoglobin sample will be determined the day after surgery. The need for transfusion, blood loss during surgery (aspirate the blood content), surgical time, hospital stay, symptom improvement and complications will be assessed.

In addition, clinical data on the patients will be collected: age, height, weight, race, concomitant diseases and treatment, family history, age at menarche, tobacco and alcohol consumption, main clinic where the surgery is performed.

3.6. INFORMATION SOURCES :

To obtain the necessary information from the study, the HCIS medical records will be used.

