- 5.2. Patient recruitment:** Patients will be recruited in the pre-surgical consultation, when laparoscopic myomectomy is indicated, randomizing both groups by simple random sampling. An informed consent will be delivered to the patients, who have to accept and sign in order to participate in the study. Fibroids will be quantified, measured and their location described.
- 5.3. Performing the surgical act:** during the laparoscopic myomectomy, temporary occlusion of the uterine arteries will be carried out using clips in those patients who are assigned to the exposed group.
- 5.4. Data collection: the pre-surgical hemoglobin determination** will be collected through the preoperative analysis and another post-surgical hemoglobin sample will be determined the day after surgery. The need for transfusion, blood loss during surgery (aspirate the blood content), surgical time, hospital stay, symptom improvement and complications will be assessed ; in addition to clinical data of the patients.
- 5.5. Statistical analysis of the collected data.**

6. BIBLIOGRAPHICAL REFERENCES:

3: Bedaiwy MA. Uterine artery occlusion at myomectomy? Towards a better definition of the indications. *Fertile Sterile* . 2019 Apr;111(4):685-686. doi : 10.1016/j.fertnstert.2019.01.024. Epub 2019 Mar 8. PubMed PMID: 30853090.

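### Do sections 3.2 and 5.3 describe a narrower operation than the one the main objective evaluates?

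*Combined protocol and SAP*

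**What the plan says.** The long form, arteries plus ligaments, appears in three places that define the exposed arm:

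- Summary, main objective: "patients with temporary clamping of the uterine arteries and utero-ovarian ligaments and patients without temporary occlusion during the surgical technique".
- Summary, study population: "laparoscopic myomectomy with temporary occlusion of the uterine arteries and utero-ovarian ligaments using clips will be analyzed".
- Section 2, group description within the main objective: "one with temporary occlusion of uterine arteries and uteroovarian ligaments and one without such occlusion".

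The short form, arteries alone, appears in two:

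- Section 3.2: "exposed (patients with temporary occlusion of the uterine arteries by clips during surgery".
- Section 5.3: "temporary occlusion of the uterine arteries will be carried out using clips in those patients who are assigned to the exposed group".

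The short form also serves for the controls in the Summary population, "laparoscopic myomectomy with the traditional technique (surgery without temporary occlusion of uterine arteries", and in section 3.2, "non-exposed (patients without temporary occlusion of the uterine arteries during surgery". It is used in the study title and at the start of the section 2 objective: "To identify the efficacy of temporary occlusion of the uterine arteries during laparoscopic myomectomy by comparing blood loss". The Introduction names both structures when it presents the technique. The exclusion in section 3.4, for patients in whom clips cannot be placed at operation, names no structure.

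**The concern.** Occlusion is the one planned difference between the arms, so the section that instructs the surgery ought to match the objective that evaluates it. The ligaments are not mentioned anywhere in sections 3 or 5, which are the sections a surgeon or study coordinator would work from. If 5.3 were followed to the letter, the trial would estimate the effect of a narrower procedure than the one named in the main objective, and the report could attach the result to the wrong intervention.

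Two further points gave this some weight. The 3.4 exclusion depends on what clipping means, so a patient whose arteries can be clipped but whose ligaments cannot is not clearly in or out. And the perioperative items listed in 3.5 and 5.4 do not record which structures were clipped, so the planned variables alone would not show which procedure was done.

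**Working it through.** No calculation decides this point. The check is a comparison of wordings, followed by a check on whether any planned number depends on them.

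**1. Count of wordings.** Taking every place that describes the intervention or an arm by structure:

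| Place | Form |
|---|---|
| Title | short |
| Summary, main objective | long |
| Summary population, exposed | long |
| Summary population, control | short |
| Introduction | long |
| Section 2, opening words | short |
| Section 2, group description | long |
| Section 3.2, exposed | short |
| Section 3.2, non-exposed | short |
| Section 5.3 | short |

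That is 4 long and 6 short. Restricted to places that define or instruct the exposed arm, it is 3 long (Summary twice, section 2) and 2 short (3.2, 5.3).

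**2. Are the two forms used for the same thing?** In two cases both forms stand in one sentence. The section 2 objective opens with the short form, then describes the two groups with the long form and refers back to it for the controls. The Summary population sentence gives the long form for the exposed arm and the short form for the control arm it is compared with. In both, the short form can only sensibly refer to the same procedure.

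**3. Does the literal reading work for the controls?** Taken literally, the short form in the Summary population and in 3.2 would allow a control patient to have her ligaments occluded. The Summary objective describes controls as having no temporary occlusion at all. The literal reading therefore produces a control arm that the objective rules out; the abbreviation reading does not.

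**4. Does 5.3 oppose the other sections?** It contains no word such as only, and it does not exclude the ligaments. It applies to patients assigned to the exposed group, so it relies on a definition given elsewhere. A procedure on both structures would satisfy all of these passages at once; they differ by omission. Which structures are intended remains for the investigators to say.

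**5. Does any planned figure depend on it?** The Summary gives a 0.7 g/dl difference, 80% power, 5% alpha and 37 per group, but no standard deviation (SD). The 37 therefore cannot be reproduced, only solved backwards. Assuming a two-sided test and the normal approximation,

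n = 2 × (1.960 + 0.842)² × SD² / 0.7²,

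so n = 37 gives SD = 0.7 × √(37/2) / 2.802 = 3.011 / 2.802 ≈ 1.07 g/dl.

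Allowing for rounding n up, an SD of about 1.06 to 1.07 gives 37. No term refers to the structures occluded. The planned tests in section 3.7 compare the groups in the same way under either wording.

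**The case for a change.** The best case for acting is that no available passage states that the short form is an abbreviation, and that the person carrying out the protocol reads 3.2 and 5.3, where the long form never appears. The reference list contains one title with arteries plus utero-ovarian vessels (reference 1) and one with arteries only (reference 8), so the narrower wording can name a procedure in its own right. The remedy would cost a few words and one data field.

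The first part stands: the abbreviation is inferred, and the annex with the study-specific consent was not available to confirm it. The titles show that both procedures have been published, but nothing about what this protocol means. The missing field is a separate request. The lists in 3.5 and 5.4 are mainly outcomes, no stated rule requires the structures to be recorded there, and adding the field would correct no error. The uncertainty in 3.4 is a gap of detail that is settled once the same meaning is applied there as elsewhere.

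**Conclusion.** The difference in wording is real, but it does not make the plan unsound. Its size is two short-form passages against three long-form ones for the exposed arm, with no demonstrated effect on power, bias, the 0.7 g/dl assumption or the analysis, and no evidence in the documents that practice varies.

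This conclusion rests on reading the short form as an abbreviation. The two mixed sentences, the title and the description of the controls support that reading, though nothing states it outright. It also rests on the available text, since the annex could not be seen. If the investigators did mean two different procedures, the passages would have to be reconciled and the conclusion would change.

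On the text as it stands, a competent team would read the sections together and reach one meaning. Making the wordings agree is routine editing that could accompany any other revision; it alters neither the design nor the analysis.
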